Cover Page

Study Protocol

Study Title: Unilateral Strength Training and Mirror Therapy for Enhancing Upper Limb Motor Function Post Stroke: A Pilot Randomised Controlled Trial

Document creation date: March 20th 2015

NCT number [not yet assigned].

Identifiers: [NCT ID not yet assigned]

Study Protocol for Unilateral Strength Training and Mirror Therapy for the Upper Limb in Chronic Stroke Patients ([name], IT Sligo, Ireland).

Assessments will take place in the Institute of Technology Sligo, in the health science physiology laboratory located in the main building on campus. The principal researcher/ research student [name] along with a second exercise professional will call to participants' homes for approximately 30 minutes per day, 3 days per week for 4 weeks to instruct and supervise the training intervention. A total of 32 participants will be randomly assigned to one of two conditions.

For the duration of the intervention participants will be seated on a standard chair in front of a standard table. They will be asked to wear a loose fitting top so that the fabric can be rolled above the elbow joint and to take off any jewellery. The participant's less-affected (LA) upper limb will be strapped into a custom made arm brace consistently holding the elbow joint at an 85° angle, the more-affected (MA) arm will rest on the table. The warm-up includes 1 minute of dynamic elbow extensions without resistance and 1 set of 5 repetitions of unilateral (LA side) isometric elbow extensions performed at perceived 50% of maximal voluntary contractions. According to maximal strength training guidelines, the main part of the training programme consists of 4 sets of 5 maximal effort isometric elbow extensions (LA limb only) held for 5 seconds with 5 seconds rest between repetitions and 3 minutes rest between sets. The principal researcher will verbally guide each participant through the intervention. Participants in the experimental group will observe the reflection of the LA training limb in a Perspex mirror placed in their mid-sagittal plane. The angle of the mirror can be adjusted according to participant preference to gain a full view of the LA limb. Prompts to focus on the reflection in the mirror will be given before each set. Participants in the control group will exercise without a mirror entirely.

Cover Page

Statistical Analysis Plan

Study Title: Unilateral Strength Training and Mirror Therapy for Enhancing Upper Limb Motor Function Post Stroke: A Pilot Randomised Controlled Trial

Document creation date: March 20th 2015

NCT number [not yet assigned].

Identifiers: [NCT ID not yet assigned]

Statistical Analysis Plan for Unilateral Strength Training and Mirror Therapy for the Upper Limb in Chronic Stroke Patients ([name], IT Sligo, Ireland).

Data were analysed using the Statistical Package for Social Sciences (SPSS) for Windows (Version X, Chicago, IL, USA). All variables were tested for conformity to normal distribution using a combination of the visual method (histograms) and the Shapiro-Wilk test. Demographic characteristics and outcome variables are described as mean \pm SD. Possible differences between groups at baseline were analysed using the independent-t-test, Mann-Whitney U test or Chi-square test. Between group differences (ST vs MST) in change from T1 to T2 and in change from T1 to T3 were determined using the independent-sample-t-test (normal distribution) or the Mann-Whitney U test (non-normal distribution or non-continuous scale). Within group differences (T1 vs T2/ T1 vs T3) were determined using the paired-sample-t-test (normal distribution) or the Wilcoxon Signed Rank Test (non-normal distribution or non-continuous scale). P-values < 0.05 were considered to be statistically significant. Between group effect sizes, the difference in means and pooled SD was calculated using an online calculator (<https://www.uccs.edu/~lbecker/>) for parametric tests or $r=Z/\sqrt{n}$ for non-parametric tests. Within group effect size was calculated as paired differences Cohen's $d = \text{mean}/Sd$ for parametric tests or $r=Z/\sqrt{n}$ for non-parametric tests. Values for Cohen's $d = 0.2, 0.5$, and 0.8 were interpreted as small, medium, and large respectively; $0.1, 0.3$, and 0.5 were defined as small, medium and large for r .

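### For continuous outcomes a normality check on the trial data chooses both the test and the effect metric, so neither is fixed in advance, and the d and r labels do not line up at medium and large

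*SAP*

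**What the plan says.** The SAP is a single unnumbered section. Its normality step reads: "All variables were tested for conformity to normal distribution using a combination of the visual method (histograms) and the Shapiro-Wilk test". It gives no threshold for Shapiro-Wilk and no rule for when histogram and test disagree. It does not say whether raw scores, change scores or each arm separately are examined.

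The result then selects the test. Between groups the comparison concerns "Between group differences (ST vs MST) in change from T1 to T2 and in change from T1 to T3". It uses the independent t-test if the data look normal and otherwise "the Mann-Whitney U test (non-normal distribution or non-continuous scale". Within groups it uses the paired t-test or "the Wilcoxon Signed Rank Test (non-normal distribution or non-continuous scale". Non-continuous scales go to the rank test whatever the normality result, so only continuous outcomes pass through the gate.

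The effect size follows the test. On the parametric route, "Between group effect sizes, the difference in means and pooled SD was calculated using an online calculator"; and "Within group effect size was calculated as paired differences" Cohen's d, the mean divided by the SD. On either rank route it is r = Z/√n, with n not defined. The cut-offs for d are 0.2, 0.5 and 0.8 ("0.8 were interpreted as small, medium, and large respectively"). For r they are 0.1, 0.3 and 0.5 ("0.5 were defined as small, medium and large for r"), one set for both between-group and within-group effects.

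The Protocol gives a total of 32 participants and no allocation ratio. Neither document names the outcomes or their scales.

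**The concern.** A t-test addresses a difference in means, and a rank test addresses a shift in ranks. When a check on the same data chooses between them, the quantity being estimated is settled only after the data are seen. The same outcome may then be reported as d for T1–T2 and as r for T1–T3. With about 16 per arm the check is itself noisy, so the route taken is partly chance.

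The label attached to the effect can follow the route, because the two sets of cut-offs are not equivalent. Effect sizes are a natural output for readers of a trial titled a pilot, so the metric should not depend on a preliminary test.

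**Working it through.** The documents state 32 participants without an effect size, SD or power, so there is no figure of the plan's own to reproduce. The check puts d and r on one scale and then simulates the gate.

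**Inputs.** The cut-offs come from the SAP and the total of 32 from the Protocol. Assumptions: 16 per arm with no dropout; Shapiro-Wilk at 0.05 applied to the change scores, either in each arm (rank route if either arm fails) or pooled after centring by arm; no histogram step. 'Moderate skew' means lognormal with sigma 0.5, standardised and shifted.

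**1. Between groups.** The expected Mann-Whitney Z for normal data is 16×16×[Φ(d/√2) − 0.5] / √(256×33/12) = 256×[Φ(d/√2) − 0.5] / 26.53. Then r = Z/√32 = 1.706×[Φ(d/√2) − 0.5].
- d 0.2: 1.706 × 0.0562 = 0.096
- d 0.5: 1.706 × 0.1382 = 0.236, 'medium' by d and 'small' by r
- d 0.8: 1.706 × 0.2142 = 0.365, 'large' by d and 'medium' by r

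Inverted, r of 0.1, 0.3 and 0.5 corresponds to d of 0.21, 0.645 and 1.156. The parametric conversion d = 2r/√(1 − r²) gives 0.20, 0.63 and 1.15.

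**2. Within groups, 16 pairs.** E[W] = 16Φ(d) + 120Φ(√2·d), the null mean is 68, and the null SD is √(16×17×33/24) = √374 = 19.34.
- d 0.5: E[W] = 102.3 and Z = 34.3/19.34 = 1.77, so r = 1.77/√16 = 0.443 (n as pairs) or 1.77/√32 = 0.313 (n as observations).
- d 0.8: Z = 2.54, so r = 0.635 or 0.449.

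| r cut-off | d between groups | paired d, n = pairs | paired d, n = observations |
|---|---|---|---|
| 0.3 | 0.645 | 0.324 | 0.475 |
| 0.5 | 1.156 | 0.578 | 0.956 |

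Against d cut-offs of 0.5 and 0.8, r tends to give the lower label between groups and the higher label within groups if n means pairs. The two readings of n differ by a factor of √2 = 1.41.

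**3. Label changes under the gate** (10,000 simulated trials per case). The entries are trials sent to the rank route whose label then differs from the d label.

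| | Normal, d 0.5 | Normal, d 0.8 | Skew, d 0.5 | Skew, d 0.8 |
|---|---|---|---|---|
| Between, either-arm check | 4.3% | 4.5% | 27.3% | 23.0% |
| Between, pooled check | 1.7% | 2.0% | 28.7% | 24.5% |
| Within, n = pairs | 3.3% | 1.8% | 23.3% | 24.7% |
| Within, n = observations | 1.4% | 1.0% | 10.2% | 10.7% |

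At true d of 0.2 with normal data (6,000 trials), the between-group rates are 2.9% (either arm) and 1.3% (pooled). Normal data are sent to ranks in 9.7% of trials (either arm) or about 5% (pooled). A single skewed sample of 16 is flagged only 41% of the time.

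**4. Type I error of the gated between-group test** (15,000 null trials each for normal, lognormal 0.5 and lognormal 1): 4.9%, 5.2% and 4.9% with the either-arm check; 5.0%, 5.1% and 5.0% pooled.

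**5. Comparator.** Two replicate normal-data trials that both use d receive different labels in 73% of cases at true d of 0.5 and 63% at 0.8.

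**6. Gain from adjusting for T1.** With equal SD σ at T1 and follow-up and correlation ρ, the variance ratio of the adjusted model to the change score is σ²(1 − ρ²) / [2σ²(1 − ρ)] = (1 + ρ)/2. The CI width ratio is the square root of this: √0.75 = 0.866 at ρ = 0.5 and √0.95 = 0.975 at ρ = 0.9. In 8,000 simulated trials at 16 per arm the ratios were 0.881 and 0.993, that is, about 12% and 1% narrower.

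**The case against.** The strongest reply is that little follows from this. Type I error is essentially nominal, no planned comparison is invalidated, and the SAP attaches no decision to the words small, medium and large. The numerical d or r is still calculated. Outcomes are summarised as mean and SD without restriction to normal data, so group means stay visible on the rank route. Sampling noise between replicate trials moves the label far more often than the gate does. All of this stands, and it keeps the point minor.

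Three stronger readings are tempting, and the documents do not support them.
- A reader might infer that labels would be wrong in some 40–55% of trials. Computing both metrics on the same normal data does give different labels in 39% (d 0.5) and 47% (d 0.8) between groups, and in 57% and 39% within groups with n as pairs. But the SAP computes one metric per test, so those rates are counterfactual.
- A reader might infer that the cut-offs disagree throughout. Between groups 'small' nearly agrees (d 0.2 gives r 0.096 against 0.1).
- A reader might treat every changed label under skew as an error. There d and r target different quantities, so a change is not by itself a mistake. The degree of skew is also an assumption that nothing in the documents supports.

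It is also fair to say that the simulated gate is more mechanical than the one written. The number of outcomes exposed to it is unknown, since non-continuous scales bypass it. Finally, adjustment for T1 addresses precision rather than the gate; fixing the change-score t-test in advance would also remove the gate. That is correct. Adjustment is recommended because it is cheap, and its gain may be small.

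**Conclusion.** The point holds as a minor one. For continuous outcomes, test and metric are chosen from the trial data by a rule that is not fully specified, so the quantity estimated is not prespecified and may differ between the two time contrasts. Between groups the label scales diverge at medium and large only. Within groups the divergence depends on an n that the SAP leaves undefined.

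The between-group label changes in about 2–5% of normal-data trials and about 23–29% under moderate skew, at true d of 0.5–0.8. These rates rest on equal arms of 16, Shapiro-Wilk at 0.05 on change scores, and no histogram step. They are illustrations of scale, not predictions for this trial. Nothing here shows an inflated error rate or an invalid comparison.

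**What to change.** Drop the normality gate. For each outcome name one method and one effect metric according to its measurement scale, the same for T1–T2 and T1–T3.

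- **Continuous outcomes, between groups:** a linear model for the follow-up value adjusted for the T1 value, reporting the mean difference with 95% CI.
- **Continuous outcomes, within groups:** the paired mean change with 95% CI.
- **Non-continuous scales:** keep rank methods. For continuous outcomes a rank analysis may be added as an optional sensitivity analysis, labelled secondary.
- **Reporting:** state whether n in the within-group r means pairs or observations.

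The cost is a small rewrite of the test and effect-size sentences and one degree of freedom (residual 32 − 2 = 30 becomes 29). No new data are needed because T1 is already collected. The gain in precision depends on the correlation between T1 and follow-up, which the documents do not give: a 95% CI about 12% narrower than the change-score t-test at 0.5, and about 1% narrower at 0.9.

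### The SAP summarises every outcome as mean ± SD, including those it tests by ranks, so for those outcomes the planned summary does not match what the test compares

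*SAP*

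**What the plan says.** The SAP is a single unnumbered section. Its descriptive rule is "Demographic characteristics and outcome variables are described as mean \pm SD". The sentence before it says that "All variables were tested for conformity to normal distribution using a combination of the visual method (histograms) and the Shapiro-Wilk test", but the result of that check is used only to choose a test, not a summary.

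Between-group comparisons of change (T1 to T2, T1 to T3) use the independent t-test or "the Mann-Whitney U test (non-normal distribution or non-continuous scale)". Within-group comparisons use the paired t-test or "the Wilcoxon Signed Rank Test (non-normal distribution or non-continuous scale)". The effect size paired with either rank test is r = Z/√n, read against cut-offs of 0.1, 0.3 and 0.5. Baseline differences may also be tested by Chi-square.

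The Protocol gives the size: "A total of 32 participants will be randomly assigned to one of two conditions". Neither document names the outcome measures, states the allocation ratio, or provides for a median, IQR, frequency count, rank-based shift or confidence interval.

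**The concern.** The SAP foresees outcomes for which it does not trust a comparison of means, and then describes those same outcomes only by a mean and SD. A rank test asks whether a patient in one arm tends to change more than a patient in the other; a mean of skewed values or scale codes answers a different question. At this sample size two or three large changes can set the mean. The quantity r has no scale units and no stated sign convention, so it does not tell the reader how far patients moved or how many improved.

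For a pilot, descriptive estimates are a main product. For a rank-tested outcome, the planned output would leave the reader unable to recover the clinical meaning of the change and, in some data sets, with a mean difference and a test that disagree in direction.

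There is a smaller mismatch of the same kind at baseline: characteristics suited to a Chi-square test cannot be described by a mean and SD.

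**Working it through.** The documents state no power, SD or expected effect, so there is no figure of the plan's own to reproduce. The check asks whether, and how often, the planned summary and the planned rank test can disagree.

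**Inputs.** From the documents: 32 participants, two arms, Mann-Whitney on change, r = Z/√n, significance at 0.05. Assumed: 16 per arm, a two-sided test, n = 32 in r. MST is read as the mirror arm and ST as the arm without a mirror. All data below are illustrative.

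**Step 1: one constructed outcome.**

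- MST change: 13 patients at 0, 3 at +6. Mean 18/16 = 1.125, SD 2.42, median 0, 3/16 improved.
- ST change: 4 patients at 0, 12 at +1. Mean 12/16 = 0.75, SD 0.45, median 1, 12/16 improved.
- Difference in means: 1.125 − 0.75 = 0.375, favouring MST.
- U for MST: 3 × 16 wins + ½ × (13 × 4) ties = 48 + 26 = 74, against 128 under no difference.
- Tie term: Σ(t³ − t) for tie groups of 17, 12 and 3 = 4896 + 1716 + 24 = 6636.
- SD of U = √{(256/12) × [33 − 6636/(32 × 31)]} = 23.69.
- Z = (74 − 128)/23.69 = −2.28, P = 0.023, |r| = 2.28/√32 = 0.40, favouring ST.

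All 18 points in the MST arm come from three patients. Had one of them not changed, the MST mean would be 12/16 = 0.75, identical to ST.

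A second constructed outcome reverses more strongly. MST has 8 patients at 2 and 8 at 3 (mean 2.50 ± 0.52). ST has 5 at 0, 8 at 1, and one each at 14, 15 and 16 (mean 3.31 ± 5.83). The means favour ST; Mann-Whitney favours MST with U = 208 of 256, Z = 3.09, P = 0.002, r = 0.55. The medians, 2.5 and 1, agree with the test.

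**Step 2: how often.** 20,000 simulated trials per scenario at 16 per arm, counting those in which the mean difference and U − 128 had opposite signs.

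| Scenario | Opposite signs, all trials | Opposite signs, trials with rank P < 0.05 |
|---|---|---|
| Normal, no effect | 7.0% | 0% |
| Normal, d = 0.5 | 2.8% | 0% |
| Skewed 5-level scale, no effect | 5.9% | 0% |
| Skewed 5-level scale, shift | 2.3% | 0% |
| Lognormal, no effect | 20.7% | 1.3% |
| Lognormal, shift of 0.5 on the log scale | 9.8% | 0.4% |
| Poisson(2) v mixture with 20% responders | 40.5% | 1.9% |
| Lognormal, different spread (medians 1.65 v 1.00, means 1.87 v 2.18) | 45.5% | 15.9% |

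**Step 3: would medians alone be enough?** No. Take 9 patients at 0 and 7 at +2 against 15 at 0 and 1 at +1. Both medians are 0. U = 7 × 16 + ½ × (9 × 15) = 179.5; the SD of U is 20.0, Z = 51.5/20.0 = 2.575, P = 0.010. The Hodges-Lehmann difference is also 0, because 9 × 15 = 135 of the 256 pairs differ by zero. The probability that a patient in the first arm does better, ties counted half, is 179.5/256 = 0.70, and the counts improved are 7/16 against 1/16. Those two summaries show the effect.

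**The case against.** The strongest reply is that reversal is rare and the examples are built to produce it. That stands. A reader might infer that the planned table is likely to contradict the planned test. The documents do not support this: they name no outcome, so neither the scale lengths nor the shape of the data is known, and the simulations show reversal beside a significant rank test to be uncommon unless the arms differ in spread. The 5-level scenarios, the nearest to a short ordinal scale, gave 0%. A bounded 0–4 example did reverse (means 1.12 v 1.25, with the rank comparison the other way), but only at P = 0.053, which is not significant under the SAP. The +6 changes in the first example also sit awkwardly on a short scale.

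A second reply is that the printed SDs would warn a careful reader. 1.13 ± 2.42 beside 0.75 ± 0.45 suggests a few extreme values, and a t-test on those data gives P = 0.55. This is fair, but a warning does not supply the missing description.

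Third, the SAP does report r, which is derived from the rank test itself. This too is fair, and it means the mean is not the only quantity given. It does not supply location, spread or numbers improved.

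Finally, the SAP does not forbid medians or counts, and they could be added later from the same data. That limits the seriousness, but the rule as written is unconditional.

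**Conclusion.** The point holds as a reporting flaw. For every outcome that goes to a rank test, the planned mean ± SD does not describe what the test compares, can be driven by two or three patients, and is accompanied only by a unit-free effect size. Disagreement in direction is possible but uncommon where it matters most: 0% to 1.9% of trials with a significant rank test in seven of the eight scenarios, and 15.9% in the one with unequal spread. The case does not depend on reversal, because the mismatch remains when the directions agree.

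No test, P-value or planned comparison is affected. The figures rest on 16 per arm, a two-sided 0.05 level and illustrative distributions, none of which the documents state. How many outcomes are affected cannot be determined, because the outcomes are not named.

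**What to change.** Tie the descriptive summary to the test:

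- Keep mean ± SD for outcomes compared by t-test.
- For every outcome compared by Mann-Whitney or Wilcoxon, report by arm the median (IQR) at T1, T2 and T3 and of each change (T1–T2, T1–T3).
- For the between-group comparison of those outcomes, add a Hodges-Lehmann difference or P(MST > ST), ties counted half, with a 95% CI. Where ties are heavy, prefer the latter, because the median and the Hodges-Lehmann difference can both be zero when the test is significant.
- Where a scale has many ties or unchanged patients, add the numbers improved, unchanged and worse, stating for each scale which direction is better.
- Report categorical characteristics, those compared by Chi-square, as n (%).

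The cost is a few sentences in the SAP and slightly longer tables. No further data are needed, and the tests stay as they are.

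### Significance tests for baseline differences between randomised arms cannot show whether the arms are balanced; standardised differences and a T1-adjusted estimate should replace them

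*SAP*

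**What the plan says.** The protocol (single unnumbered section) states that "A total of 32 participants will be randomly assigned to one of two conditions". It gives no allocation ratio.

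The SAP (single unnumbered section) contains four relevant statements:

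- Baseline comparison: "Possible differences between groups at baseline were analysed using the independent-t-test, Mann-Whitney U test or Chi-square test".
- Threshold: "P-values < 0.05 were considered to be statistically significant". Sidedness is not stated, and no multiplicity adjustment is described.
- Treatment comparison: "Between group differences (ST vs MST) in change from T1 to T2 and in change from T1 to T3 were determined using the independent-sample-t-test", or the Mann-Whitney U test. No baseline covariate is named.
- Effect sizes: Cohen's d values of 0.2, 0.5 and 0.8 "were interpreted as small, medium, and large respectively".

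The SAP does not say what follows from a significant or a non-significant baseline test. It does plan descriptive summaries: "Demographic characteristics and outcome variables are described as mean" with SD.

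**The concern.** A significance test asks whether chance alone could explain a difference. Under random allocation the answer is known beforehand: chance is the explanation, unless allocation failed, and the SAP does not give a check on allocation as the purpose. The useful question is whether an imbalance in a prognostic variable is large enough to affect how the trial result is read. A P-value does not answer it, because it depends on sample size and takes no account of how strongly the variable relates to outcome.

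With 32 participants, sizeable chance imbalances will often be non-significant, and a reader may take that as evidence that the arms are comparable. Conversely, an unimportant variable may be flagged. The treatment comparison uses unadjusted change scores, so these tests are the only formal look at comparability in the plan.

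**Working it through.** **Inputs.** From the documents: 32 randomised, two conditions, P < 0.05, and 0.5 and 0.8 as medium and large d. Assumed because not stated: 16 per arm, two-sided tests, the number of baseline variables (3 to 10, treated as independent), and the correlation between a baseline variable and the analysed outcome (0.2 to 0.7). The documents give no figure of their own to reproduce.

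**1. Smallest observed difference that reaches significance (t-test).**

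- Formula: d = t(0.975, N − 2) × √(1/n1 + 1/n2).
- 16 vs 16: 2.0423 × √(2/16) = 2.0423 × 0.3536 = 0.722 SD.
- Unequal splits: 0.73 at 14:18 and 0.75 at 12:20.
- Fewer analysed: 0.78 at 14 per arm and 0.85 at 12 per arm.
- One-sided: about 0.60.

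An observed difference of 0.50 SD gives t = 0.50/0.3536 = 1.41 and P = 0.168. A difference of 0.70 SD gives t = 1.98 and P = 0.057. A medium imbalance on the SAP's scale, and one approaching large, are therefore both non-significant.

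The 0.72 SD figure applies to the t-test only. For a binary characteristic with 16 per arm and no continuity correction, 8 vs 13 (50% vs 81%) gives chi-square 3.46 and P = 0.063.

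**2. How often this happens by chance.** For one variable under randomisation, P(|d| > 0.50) = 0.168 and P(|d| > 0.722) = 0.050. The chance of a non-significant imbalance of 0.50 to 0.72 SD is 0.168 − 0.050 = 0.118. Over k independent variables:

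| k | At least one chance significant result, 1 − 0.95^k | At least one non-significant imbalance of 0.50 to 0.72 SD, 1 − 0.882^k |
|---|---|---|
| 3 | 14% | 31% |
| 5 | 23% | 47% |
| 8 | 34% | 63% |
| 10 | 40% | 71% |

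**3. A separate matter: the unadjusted treatment comparison.** Suppose a baseline variable has correlation ρ with the analysed change and is imbalanced by D. The expected arm difference under no treatment effect is then ρ × D; for example, 0.5 × 0.70 = 0.35 SD. Simulation (200,000 trials per setting, 16 per arm) gives the false-positive rate conditional on that imbalance:

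| ρ | D = 0.50 SD | D = 0.70 SD |
|---|---|---|
| 0.2 | about 5% | about 6% |
| 0.5 | about 7% | about 12 to 13% |
| 0.7 | about 8 to 9% | about 20% |

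Rough check for ρ = 0.5 and D = 0.70: the shift is 0.35/0.3536 = 0.99 standard errors, and the conditional SD of the statistic is √(1 − 0.25) = 0.866. So 1 − Φ((2.042 − 0.99)/0.866) is about 11%, near the simulated value. Averaged over all randomisations the rate stays at 5%.

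**4. Which ρ applies to the T1 value itself.** With equal variances at both visits and a pre-post correlation r, the correlation of T1 with change is −√((1 − r)/2). That is 0.50 in size at r = 0.5, 0.39 at r = 0.7 and 0.22 at r = 0.9. For a T1 imbalance, the ρ = 0.2 to 0.5 rows are therefore the relevant ones. The documents give no value of r.

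**The case against.** The strongest reply is that the SAP attaches no decision to the baseline tests. It does not treat non-significance as proof of balance, and it plans no adjusted model. A reader might infer that baseline P-values select covariates, or that the tests distort the ST vs MST result. The documents support neither: deleting the tests would leave the planned treatment comparison unchanged.

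A reader might also attribute the conditional error rates of up to about 20% to the baseline tests. That is wrong too. Those rates belong to the unadjusted change-score test and would persist without any baseline testing. The highest of them pair a near-maximal non-significant imbalance with a high assumed correlation; at a correlation of 0.2 the rate is 5 to 6%.

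It is also fair to say that means and SDs are already planned. If they are shown by arm, which is the natural reading though not explicit, a reader could work out standardised differences. Finally, the 0.72 SD is a property of the t-test at this sample size, not an imbalance seen in trial data.

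All of this limits the consequence. It does not give the tests a purpose: they still answer a question that randomisation has settled, and they say nothing about whether an imbalance matters.

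**Conclusion.** The point holds as a weakness of reporting and interpretation that should be corrected. It is not a bias in the treatment comparison.

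The argument that the null is true by design needs only proper randomisation. The 0.72 SD cut-off rests on 16 per arm and a two-sided t-test; unequal splits up to 12:20 move it only to 0.75. The chance-flag figures of 14% to 40% rest on 3 to 10 independent tests, a number the documents do not give.

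The lack of baseline adjustment is a related but distinct gap. Its size depends on a correlation that the documents do not supply, and it concerns error conditional on an imbalance, with the average error rate unaffected.

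**What to change.** Make four changes to the SAP:

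1. Delete the hypothesis tests comparing the arms at baseline.
2. Tabulate baseline characteristics by arm, with the standardised difference for each. The SAP already uses means, SDs and between-group effect sizes, so no new method is needed.
3. State that no adjustment will be chosen or dropped because of a baseline P-value.
4. For each continuous outcome, report an ST vs MST estimate adjusted for that outcome's T1 value, beside the change-score test at T2 and at T3. T1 values are already collected, so the covariate is fixed without searching the data.

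The SAP is written in the past tense. If the data have already been analysed, label the adjusted estimates post hoc; items 1 to 3 can still be applied in reporting.

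The cost is a change of wording and a few extra models, with no new data or participants. Each adjusted estimate uses one degree of freedom, leaving 29 of 30 with 16 per arm. Adjusting for T1 deals with imbalance in the outcome's own starting value. It does not remove imbalance in other characteristics, which the standardised differences would make visible.

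### For continuous outcomes, ANCOVA on T1 would usually estimate the MST–ST difference more precisely than the planned t-test on change, at little cost; the planned test is valid

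*SAP*

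**What the plan says.** The SAP is one unnumbered section. For normally distributed data it states that ST versus MST differences "in change from T1 to T2 and in change from T1 to T3 were determined using the independent-sample-t-test". For other outcomes it offers the alternative "or the Mann-Whitney U test (non-normal distribution or non-continuous scale".

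Its only other use of baseline in comparing the groups is a test: "Possible differences between groups at baseline were analysed using the independent-t-test, Mann-Whitney U test or Chi-square test". It does not say what follows if a difference is found, and no analysis in either document includes T1 as a covariate.

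The effect size for this comparison is described thus: "Between group effect sizes, the difference in means and pooled SD was calculated using an online calculator". It does not say whether the SD is that of T1, of follow-up or of change.

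On size, the Protocol says: "A total of 32 participants will be randomly assigned to one of two conditions". Neither document gives an SD, a correlation between T1 and follow-up, a target difference, a power, a dropout rate or a named outcome measure. I read T1 as the pre-training assessment, MST as training with the mirror and ST as training without it; the documents do not define these labels.

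**The concern.** The MST–ST comparison answers the trial's question, and T1 is already measured. Subtracting T1 from follow-up assumes that a participant one unit higher at T1 will, on average, be exactly one unit higher later. If the true slope β is below 1, as it is whenever the SDs are equal and the correlation is below 1, subtraction over-corrects. A chance T1 difference b (MST minus ST) then moves the change-score estimate by −(1−β)b. With about 16 per arm, sizeable chance differences are not rare. At stake is the width of the interval around the main estimate of a small pilot, not the validity of its P-value.

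**Working it through.** **Inputs.** N = 32 in two conditions (Protocol). Significance at 0.05 (SAP), taken as two-sided because the SAP does not say. Assumed: 16 per arm, everyone analysed, the same slope in both arms, and a normal T1 value. The correlation ρ and the SD ratio are not in the documents, so I show ranges. The plan states no figure to reproduce.

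**Step 1: variances.** Set SD(T1) = 1 and SD(follow-up) = k, so β = ρk. Apart from the common factor 2/16:

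- change score: 1 + k² − 2ρk = k²(1−ρ²) + (1−β)²
- ANCOVA, averaged over randomisations: k²(1−ρ²) × [1 + 1/(N−4)] = k²(1−ρ²) × 29/28

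The term (1−β)² is the variance contributed by the shift −(1−β)b. ANCOVA removes that term and pays the factor 29/28 for estimating the slope.

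**Step 2: ratio, ANCOVA over change.** With equal SDs (k = 1) it reduces to (29/28)(1+ρ)/2. At ρ = 0.5 this is 1.0357 × 0.75 = 0.777.

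| SD ratio k | ρ = 0.5 | ρ = 0.7 | ρ = 0.9 | ρ = 0.95 |
|---|---|---|---|---|
| 0.8 | 0.59 | 0.65 | 0.63 | 0.54 |
| 1.0 | 0.78 | 0.88 | 0.98 | 1.01 |
| 1.2 | 0.90 | 1.00 | 1.01 | 0.91 |

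With equal SDs, break-even is at (1+ρ)/2 = 28/29, that is ρ = 0.93. In general the condition is β near 1, not ρ near 1: with k = 1.2 the ratio is at or above 1 for ρ of about 0.70 to 0.91 (β 0.84 to 1.09). Simulation with 16 per arm and equal SDs gave 0.778, 0.887, 0.986 and 1.012 for the four correlations.

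**Step 3: confidence interval.** The 95% half-width in T1 SDs is t × √(variance × 2/16), with t = 2.042 (30 df) for change and 2.045 (29 df) for ANCOVA. With equal SDs it goes from 0.72 to 0.64 at ρ = 0.5, from 0.56 to 0.53 at ρ = 0.7, and is 0.32 for both at ρ = 0.9.

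**Step 4: the most ANCOVA can lose.** The ratio is largest at β = 1, where it equals 1 + 1/(N−4): 29/28 = 1.036 with 32 analysed, 21/20 = 1.05 with 24. This is an average over randomisations. In one realised sample with β = 1 the loss is t²/30, where t is the t-statistic for the T1 difference: 1/30 = 3.3% at t = 1, and 2.04²/30 = 14% at t = 2.04. It exceeds 3.6% in about 31% of samples and 13.9% in 5%.

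**Step 5: trials with a visible T1 difference.** The SD of b is √(2/16) = 0.354, so |b| exceeds 0.5 SD in about 16% of trials, with mean |b| = 0.66 in those. With equal SDs the change-score estimate is then off on average by (1−ρ) × 0.66 = 0.33, 0.20 and 0.07 SD at ρ = 0.5, 0.7 and 0.9. ANCOVA is off by about 0, but its variance in those trials is about 13% above k²(1−ρ²) × 2/16, not 3.6%.

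Both sides combine in the mean squared error. Mean b² in those trials is 3.64 × 0.125 = 0.455, so the ANCOVA/change ratio is 1.13 × (1−ρ²) × 0.125 ÷ [(1−ρ²) × 0.125 + (1−ρ)² × 0.455]. This gives 0.51, 0.69, 0.95 and 1.03 at ρ = 0.5, 0.7, 0.9 and 0.95.

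**The case against.** The strongest reply is that nothing is broken. The planned test already uses T1, is unbiased and holds its error rate (simulated type I error 0.048 to 0.051 for both methods). This is a pilot with no stated power target, and the size of the gain rests on figures that the documents do not give. If the outcome is a highly repeatable measure with β near 1, the two methods practically tie. The number of outcomes that reach the t-test is also unknown, since non-normal and non-continuous ones go to Mann-Whitney. All of this stands, and it limits the point to a recommended improvement. It does not remove the case for change: when β is unknown, the average loss is capped at a few per cent while the possible gain is several times larger.

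Three stronger readings are tempting and not supported.

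- A reader might infer that the change-score test is biased or gives a wrong error rate. Participants are randomised, so the shift −(1−β)b averages to zero over randomisations.
- A reader might infer that ANCOVA can never cost more than 4%. That cap is an average with all 32 analysed; a single imbalanced sample with β = 1 can lose more, and the cap rises with dropout.
- A reader might count tighter intervals and protection from T1 imbalance as two gains. They are one, because the variance removed is the variance of that shift.

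**Conclusion.** The point holds as an efficiency improvement for continuous, normally distributed outcomes. ANCOVA is more precise than the t-test on change unless the true slope is close to 1. With 32 analysed and equal SDs, the expected variance reduction is about 22% at ρ = 0.5, 12% at 0.7 and 2% at 0.9, with a 1% loss at 0.95. A smaller follow-up SD makes the gain larger; a larger one can remove it or turn it into a small loss. The correlations and SD ratios are assumptions, so the gain in this trial cannot be stated and may be small. Confidence is medium for that reason; the formulas themselves were confirmed by simulation.

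**What to change.** For continuous outcomes, make the between-group analysis an ANCOVA of the T2 value, and separately of the T3 value, on group and the T1 value. Apply the normality check to the model residuals. Report the adjusted MST–ST difference with its 95% CI. Prespecifying this also removes any need to decide on adjustment after seeing the baseline tests.

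Restate the between-group effect size to match and name its SD, for example the adjusted difference over the pooled T1 SD. The choice matters: with equal SDs, a difference of 0.5 T1 SDs gives d = 0.5/√(2(1−ρ)) = 0.50, 0.65 or 1.12 at ρ = 0.5, 0.7 or 0.9 on the SD of change, against 0.50 throughout on the T1 SD. This ambiguity exists whichever test is used, and I do not count it as support for ANCOVA.

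Keep Mann-Whitney and r for non-continuous or clearly non-normal outcomes. If the analysis is already done, as the SAP's past tense may suggest, ANCOVA can be reported alongside and labelled as added later.

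The cost is SAP wording, slightly more analysis work and one residual degree of freedom (30 to 29). No further data or participants are needed.
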